### 2.4 Blinding

Not applicable to this study.

### 2.5 Study Assessments

#### ODI

The Oswestry Disability Index (ODI) is a validated questionnaire of low back pain-related disability. It assesses the impact of low back pain on activities of daily living and participation and includes 10 questions. It is scored on a scale of 0 (no disability) to 100 (complete disability), with categories of 0-20 (minimal disability), 21-40 (moderate disability), 41-60 (severe disability), 61-80 (crippling back pain), and 81-100 (bed-bound or exaggerating). The minimally clinically important difference for this tool is considered to be 10 points. For the purposes of this study, this will be administered over the phone.

The ODI score will be calculated as follows:

For each section of six statements the total score is 5; if the first statement is marked the score = 0; if the last statement is marked the score = 5. Intervening statements are scored according to rank. If more than one box is marked in each section, take the highest score.

The ODI score may be summarized as:

$$\text{ODI Score} = \text{total score}/(5 * \text{number of questions answered}) * 100$$

	CD_3012_Rev B Five-Plus Year Follow-Up of SMART Trial Statistical Analysis Plan	Date Effective: November 5, 2019 Page 7 of 21
---	---	---

Scores will be rounded to a whole number for convenience.

#### Pain Score

The numeric pain rating scale that will be used for this study is a 10-point numeric scale based on the Visual Analogue Scale (VAS) pain rating questionnaire used during the SMART study, 0 being no pain and 10 being worst imaginable pain. Respondents are asked to indicate what integer on the scale corresponds to their perceived level of pain in their low back. Subjects will be specifically instructed to report their level of low back pain as an average for the last seven days. Studies have shown that a minimally clinically important difference in VAS is considered to be approximately 1.5 points. For the purposes of this study, this will be administered over the phone.

#### Patient Satisfaction

Satisfaction will be assessed with a short, non-validated questionnaire about degree of improvement, satisfaction with treatment, and willingness to repeat the treatment for the same outcome.

#### Opioids, Injections, and Interventions

Patient treatments including opioid use in the past 30 days (prior to the study visit), injections in the past 12 months (prior to study visit), and interventions post the Intratect procedure will be collected on the case report form (CRF).

### **2.6 Endpoint Adjudication**

An independent orthopaedic surgeon will review medical records and radiologic images to determine diagnosis (pain location, etiology, and nature) resulting in an intervention (procedure and/or injections). All interventions will be adjudicated as either a treatment failure (ongoing or exacerbated CLBP of similar location, etiology and nature/severity to the pre-Intratect treatment pain) or not related (different location, etiology, or nature/severity).

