5.2 Secondary Effectiveness Endpoint

Secondary effectiveness endpoints are:

- a) The mean reduction from baseline in patient reported pain.
- b) Responder rates for ODI - proportion of subjects who achieve \geq 10-point reduction in ODI from baseline to 5+ years post-treatment.
- c) Responder rates for pain rating - proportion of subjects who achieve a \geq 1.5-point reduction in pain rating from baseline to 5+ years post-treatment.
- d) The proportion of patients with surgical interventions for low back pain of the same treatment region post the Intracept procedure.
- e) The proportion of patients currently utilizing opioids for low back pain of the same treatment region.
- f) The proportion of patients utilizing injections in the past 12 months for low back pain of the same treatment region.
- g) Patient satisfaction with the Intracept Procedure.

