6 STATISTICAL ANALYSIS

6.1 Statistical Methods

Demographic and baseline characteristics will be summarized using descriptive statistics.

The mean change from baseline to five years in the ODI is the primary endpoint for this study. Statistical differences will be tested using Student's t-test. An analysis of covariance will also be performed using baseline characteristics and ODI measurements.

Secondary endpoints will be summarized using descriptive statistics.

- Mean reduction in pain rating baseline to 5+ years.
- Responder rates for ODI will be determined by the proportion of subjects who achieve \geq 10-point reduction in ODI from baseline to 5+ years post-treatment.
- Responder rates for pain rating will be determined by the proportion of subjects who achieve a \geq 1.5-point reduction in pain rating from baseline to 5+ years post-treatment.

- Number and rate of surgical interventions post-procedure, as adjudicated by an independent reviewer.
- The proportion of patients currently utilizing opioids for low back pain of the same treatment region.
- The proportion of patients utilizing injections in the past 12 months for low back pain of the same treatment region.
- Patient satisfaction with the Intracept Procedure at 5+ years.

No imputations will be made for missing data.

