#### **3.1.2 Secondary Efficacy Endpoints**

The secondary efficacy endpoints are:

	CD_3012_Rev B Five-Plus Year Follow-Up of SMART Trial Statistical Analysis Plan	Date Effective: November 5, 2019 Page 8 of 21
---	--	--

- The mean reduction from baseline VAS in patient reported pain score (10-point VAS-based numeric pain score) at 5+ years post treatment.
- Responder rates for ODI - proportion of subjects who achieve  $\geq$  10-point reduction in ODI from baseline to 5+ years post-treatment.
- Responder rates for pain rating - proportion of subjects who achieve a  $\geq$  1.5-point reduction in pain rating (VAS) from baseline to 5+ years post-treatment.
- The number and proportion of subjects in each quartile ( $\leq$  24%, 25-49%, 50-74%, and 75-100%) for percent ODI reduction
- The number and proportion of subjects in each quartile ( $\leq$  24% or less, 25-49%, 50-74%, and 75-100%) for percent VAS-based pain score reduction.
- The number and proportion of subjects with procedures for low back pain of the same Intracept treatment region post procedure.
- The number and proportion of subjects actively utilizing opioids for low back pain of the same treatment region (defined as  $>$  25% of total dosage in 30 days prior to study visit).
- The number and proportion of subjects utilizing injections in the past 12 months for the treatment of low back pain of the same Intracept treatment region.
- Patient satisfaction with the Intracept Procedure.
- Composite endpoint of long term treatment success defined as:
  - ODI decrease of 10 or more at 5+ years
  - VAS-based pain score decrease of 2 or more at 5+ years
  - Not actively using opioids for LBP (defined as  $>$  25% of total dosage used in 30 days prior to study visit)
  - No LBP procedures since the Intracept procedure (that is adjudicated as treatment failure due to same location, same etiology, same severity as baseline)
  - Not actively utilizing injections for low back pain treatment (in past 12 months and adjudicated as for same location, etiology, severity as baseline)

No safety endpoints were collected in this post market study.

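### Under SAP 2.6 a difference in pain severity alone can take a same-site, same-etiology re-intervention out of treatment failure, which exposes the composite success rate

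*SAP*

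**What the plan says.** SAP 2.6 has an independent orthopaedic surgeon review records and images "to determine diagnosis (pain location, etiology, and nature) resulting in an intervention (procedure and/or injections"). Severity is not among the things to be determined.

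Two labels follow. "All interventions will be adjudicated as either a treatment failure", meaning "ongoing or exacerbated CLBP of similar location, etiology and nature/severity to the pre-Intratect treatment pain", or as "not related (different location, etiology, or nature/severity"). No third category, tolerance, direction or order of precedence is given.

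SAP 3.1.2 carries severity into the composite. A procedure counts against success only if "adjudicated as treatment failure due to same location, same etiology, same severity as baseline", and an injection only if "in past 12 months and adjudicated as for same location, etiology, severity as baseline". The success definition printed under Table 15 repeats both conditions.

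Other places judge the same events without severity:

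- Protocol 5.2(d): "The proportion of patients with surgical interventions for low back pain of the same treatment region post the Intracept procedure".
- The stand-alone procedure and injection endpoints in SAP 3.1.2, which use the treatment region.
- The Table 15 re-intervention row, which uses location and etiology.
- The Table 15 injection row, which uses treatment location.

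**The concern.** Severity does not tell whether a later intervention was for the pain that was originally treated; location and etiology do. In SAP 2.6 severity can nevertheless decide the label by itself, because the second label joins its conditions with *or*.

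The patients affected are those with partial relief who are later re-treated at the same site for the same cause. A durability study should be able to count this incomplete-response group. If such a patient has, say, a fusion for milder residual pain and scores well at the 5+ year call, the composite can record a success for the original procedure, although the ODI and pain scores were taken after the second procedure. For milder pain, relabelling can only raise the success rate.

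**Working it through.** The plan states no expected re-intervention rate and no figure for the composite, so there is nothing to reproduce. The check is a reading of the rules side by side, followed by a scale calculation.

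**Step 1. All combinations.** Treat location, etiology and severity each as same or different from baseline, which gives 8 combinations.

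| Location | Etiology | Severity | SAP 2.6, read literally | Table 15 re-intervention row |
|---|---|---|---|---|
| same | same | same | failure | counted |
| same | same | different | not related | counted |
| the other 6 combinations | | | not related | not counted |

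The two rules disagree on one combination only: same site, same etiology, different severity.

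**Step 2. Direction of the severity difference.** Take three patients re-treated for pain of the same location, etiology and nature.

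- Pain at about the baseline level: failure under the first label, with no conflict.
- Pain milder than baseline: failure if the adjudicator regards it as ongoing and similar, not related if the severity difference is taken at its word. The text does not settle which.
- Pain worse than baseline: failure because it is exacerbated, and not related because its severity differs. Both labels apply.

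**Step 3. Can severity be judged?** Protocol 7.4 and 7.5 record the date, type and location of each injection and intervention, not the pain level at that time. The severity test therefore depends on what the medical records happen to contain.

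**Step 4. Effect inside Table 15.** A milder-pain patient labelled not related is counted in the re-intervention row, and so among subjects with any failure criterion. The same patient can meet every condition of the success definition below it. The two summary rates then need not add to 100%.

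**Step 5. Size per patient.** Shift in the success rate = 1/N.

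- N = 133 (SAP 2.1): 1/133 = 0.75 points; five patients, 5/133 = 3.8 points. With the N = 132 in the Table 1 shell, 1/132 = 0.76.
- N = 80 attending (assumed): 1/80 = 1.25 points; five patients, 5/80 = 6.3 points.

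**Step 6. Size under assumed rates.** Overstatement = (share with a same-site, same-etiology event) × (share milder and labelled not related) × (share passing the other components). All inputs are assumptions.

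- Share milder: let pain at re-treatment minus baseline be normal with mean −1 and SD 2, with *similar* meaning within 1.5 points. Then P(below −1.5) = Φ((−1.5 + 1)/2) = Φ(−0.25) = 0.40. The share worse is 1 − Φ((1.5 + 1)/2) = 1 − Φ(1.25) = 0.11.
- Central case, milder only: 0.15 × 0.40 × 0.50 = 0.030, or 3.0 points. At N = 133 that is 0.030 × 133 ≈ 4 patients.
- Range of the milder share, for mean 0 to −2, SD 1.5 to 2.5 and tolerance 1 to 2: lowest Φ(−2/1.5) = 0.09, highest Φ((−1 + 2)/1.5) = 0.75.
- Low end: 0.05 × 0.09 × 0.30 = 0.1 points. High end: 0.20 × 0.75 × 0.70 = 10.5 points.

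**The case against.** **Adjudicator discretion.** The failure label speaks of ongoing pain and of similarity rather than identity, and nature/severity is a single slashed item. A surgeon could reasonably call residual pain at the same site ongoing. This stands: a reader might infer that every milder case must be labelled not related, and the text does not go that far. But nothing requires the label of failure either, and the composite asks for the same severity outright, as a condition of its own.

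**Re-intervention rate.** Protocol 6.1 plans "Number and rate of surgical interventions post-procedure, as adjudicated by an independent reviewer", and a reader might infer that the reported re-intervention rate would shrink as well. The documents do not support this. Protocol 6.1 does not say that events judged not related are excluded. Protocol 5.2(d) and the same-region endpoints in SAP 3.1.2 carry no severity condition. Table 13 reports procedures without regard to severity, and the Table 15 re-intervention row does not use severity.

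**Later procedures are handled elsewhere.** SAP 4.4.2 adds an Intracept-only cohort without subjects who had additional procedures. That helps for ODI and pain, but Appendix A applies it to Tables 8 and 9 only. The composite in Table 15 is not covered.

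**A matter of choice.** Defining failure as the return of baseline-like pain is a possible choice. It would need a rule that does not give worse pain both labels and that agrees with the Table 15 row. The present text does neither.

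**Size.** Every rate in the calculation is assumed, and nothing in the documents shows how many re-treated patients would pass the other components. Some will fail on ODI, pain or opioid use anyway. This stands, and the range is too wide to establish materiality by itself.

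**Conclusion.** The concern holds for the composite success rate, one of ten secondary endpoints in SAP 3.1.2. SAP 2.6 allows severity alone to decide the label, contradicts itself for worse pain, and gives no tolerance for a quality the adjudicator is not asked to determine. The composite and the Table 15 success definition carry the condition; the Table 15 re-intervention row does not.

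The firm part of the size is 0.75 points per affected patient at N = 133, rising as attendance falls. About 3 points follows only if 15% have such an event, 40% of those are milder and all of these are labelled not related, and 50% of them pass the remaining components. Adding the 11% with worse pain would give a larger figure, but that group is expressly named as failure, so it should not be counted as a one-way error.

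The primary ODI endpoint does not depend on adjudication and is unaffected. The point deserves correction before analysis but does not threaten the main result.

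**What to change.** Use one rule in three places: SAP 2.6, the procedure and injection components of the composite in SAP 3.1.2, and the success definition under Table 15. Changing SAP 2.6 alone would leave the severity condition in force in the other two.

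- Treatment failure: intervention for low back pain of the same location and the same etiology/nature as before the index procedure, whatever its severity.
- Not related: different location, or different etiology/nature.

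This brings the success definition into line with the Table 15 re-intervention row on severity. State that nature is judged together with etiology, so that the row and the definition use the same terms.

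Record severity relative to baseline (milder, similar, worse, not documented) as a descriptive field where the records show it. If the sponsor wants the severity-restricted composite, report it as a labelled sensitivity row.

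The cost is wording in the SAP and the adjudication form, using events that are already to be adjudicated, with no further patient contact. The downside is that the composite success rate may be slightly lower.

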## **3. EFFICACY AND SAFETY ENDPOINTS**

### **3.1 Efficacy Endpoints**

#### **3.1.1 Primary Efficacy Endpoint**

The primary effectiveness endpoint for this study is the mean improvement in ODI from baseline to 5+ years within treatment arm subjects.

#### **3.1.2 Secondary Efficacy Endpoints**

The secondary efficacy endpoints are:

	CD_3012_Rev B Five-Plus Year Follow-Up of SMART Trial Statistical Analysis Plan	Date Effective: November 5, 2019 Page 8 of 21
---	--	--

- The mean reduction from baseline VAS in patient reported pain score (10-point VAS-based numeric pain score) at 5+ years post treatment.
- Responder rates for ODI - proportion of subjects who achieve  $\geq$  10-point reduction in ODI from baseline to 5+ years post-treatment.
- Responder rates for pain rating - proportion of subjects who achieve a  $\geq$  1.5-point reduction in pain rating (VAS) from baseline to 5+ years post-treatment.
- The number and proportion of subjects in each quartile ( $\leq$  24%, 25-49%, 50-74%, and 75-100%) for percent ODI reduction
- The number and proportion of subjects in each quartile ( $\leq$  24% or less, 25-49%, 50-74%, and 75-100%) for percent VAS-based pain score reduction.
- The number and proportion of subjects with procedures for low back pain of the same Intracept treatment region post procedure.
- The number and proportion of subjects actively utilizing opioids for low back pain of the same treatment region (defined as  $>$  25% of total dosage in 30 days prior to study visit).
- The number and proportion of subjects utilizing injections in the past 12 months for the treatment of low back pain of the same Intracept treatment region.
- Patient satisfaction with the Intracept Procedure.
- Composite endpoint of long term treatment success defined as:
  - ODI decrease of 10 or more at 5+ years
  - VAS-based pain score decrease of 2 or more at 5+ years
  - Not actively using opioids for LBP (defined as  $>$  25% of total dosage used in 30 days prior to study visit)
  - No LBP procedures since the Intracept procedure (that is adjudicated as treatment failure due to same location, same etiology, same severity as baseline)
  - Not actively utilizing injections for low back pain treatment (in past 12 months and adjudicated as for same location, etiology, severity as baseline)

No safety endpoints were collected in this post market study.

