7.4 Narcotic Medications & Injections

Patient-reported low back narcotic usage will be captured at the 5+ year follow up visit. Drug type, prescribed dosage, and average daily dose for the last 30 days will be documented on the source document worksheet.

Patient-reported injections within the last 12 months will be collected. Date, type, and location for each injection will be recorded.

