Average change in ODI in INTRACEPT group between baseline and 1 year	Mean, N, 95% CI, t-test p (Ho: $\delta=0$ )
Average change in ODI in INTRACEPT group between baseline and 2 years	Mean, N, 95% CI, t-test p (Ho: $\delta=0$ )
Average change in ODI in INTRACEPT group between baseline and 5+ years	Mean, N, 95% CI, rm F-test p (Ho: $\delta=0$ )
Time (per year) effect on ODI in INTRACEPT group	Mean, N, 95% CI, rm F-test p (Ho: time=0)
Average change in VAS in CONTROL group between baseline and 1 year	Mean, N, 95% CI, t-test p (Ho: $\delta=0$ )
Average change in VAS in CONTROL group between baseline and 2 years	Mean, N, 95% CI, t-test p (Ho: $\delta=0$ )
Average change in VAS in INTRACEPT group between baseline and 1 year	Mean, N, 95% CI, t-test p (Ho: $\delta=0$ )
Average change in VAS in INTRACEPT group between baseline and 2 years	Mean, N, 95% CI, t-test p (Ho: $\delta=0$ )
Average change in VAS in INTRACEPT group between baseline and 5+ years	Mean, N, 95% CI, t-test p (Ho: $\delta=0$ )
Time (per year) effect on VAS in INTRACEPT group	Mean, N, 95% CI, rm F-test p (Ho: time=0)

	CD_3012_Rev B Five-Plus Year Follow-Up of SMART Trial Statistical Analysis Plan	Date Effective: November 5, 2019 Page 17 of 21
---	--	---

Table 11 – Comparison of SMART Endpoints			
Characteristic	SMART Treated Subjects in 5+ Yr Follow-up N = XX	SMART Treated Subjects Not in 5+ Year Follow-up N = XX	t-test of Means or Exact Test of Proportions
Change in ODI (Baseline to 3 Months)	Mean + SD, Median, Range	Mean + SD, Median, Range	
Change in VAS (Baseline to 3 Months)	Mean + SD, Median, Range	Mean + SD, Median, Range	
ODI Responders ( $\geq$ point ODI reduction)	% (n/N)	% (n/N)	

Table 12 – Opioids & Injections Utilization	
SMART 5+ Yr Follow-up Subjects N = XX	
Opioid Use	
Subjects Taking Opioids at Baseline	% (n/N)
Subjects actively taking Opioids in last 30 days (5+ Year Follow-up Visit)	% (n/N)
Opioid Dosage (in subjects taking opioids)	
Opioid Dosage at Baseline	Mean + SD, Median, Range
Opioid Dosage at 5+ years post treatment	Mean + SD, Median, Range
Epidural Injections	
Subjects with prior injections at baseline	Mean + SD, Median, Range
Subjects with injections in 12 months prior to 5+ year post treatment visit	Mean + SD, Median, Range
Subjects with injections for low back pain treatment in the same location as Intracept treatment (in the past 12 months):	Mean + SD, Median, Range

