Mean # of injections per subject in 12 months prior to baseline	% (n/N)
Mean # of injections per subject in 12 months prior to 5+ year post treatment visit	% (n/N)
Time to first injection for low back pain in same location post Intracept Procedure	Mean + SD, Median, Range

	CD_3012_Rev B Five-Plus Year Follow-Up of SMART Trial Statistical Analysis Plan	Date Effective: November 5, 2019 Page 18 of 21
---	--	---

Table 13 – Surgical Interventions	
	SMART 5+ Yr Follow-up Subjects N = XX
Number (%) of subject reporting a procedure	% (n/N)
Number of procedures	% (n/N)
Re-intervention Rate over Time	
1 Year	S% (95% CI)
2 Year	S% (95% CI)
5 Year	S% (95% CI)
Type of procedure:	
Discectomy	% (n/N)
Lumbar fusion	% (n/N)
RF Ablation	% (n/N)
Other	% (n/N)
At the same level of Intracept treatment?	
Yes	% (n/N)
No	% (n/N)
Time to intervention (post Intracept procedure)	Mean + SD, Median, Range
Same etiology and level as Intracept treatment	Mean + SD, Median, Range
Different etiology or level from Intracept treatment	Mean + SD, Median, Range

Table 14 – Pain Status at 5 + Years	
	SMART 5+ Yr Follow-up Subjects N = XX
Pain Status	
Constant	% (n/N)
Intermittent	% (n/N)
No Pain	% (n/N)
Experiencing Pain	
Same location as prior to Intracept Procedure	% (n/N)
Different location from prior to Intracept Procedure	% (n/N)
Same nature as prior to Intracept Procedure	% (n/N)
Different nature from prior to Intracept Procedure	% (n/N)
Time (per year) effect on VAS in INTRACEPT group	Mean, N, 95% CI, rm F-test p (Ho: time=0)

	CD_3012_Rev B Five-Plus Year Follow-Up of SMART Trial Statistical Analysis Plan	Date Effective: November 5, 2019 Page 19 of 21
---	--	---

Table 15 – Durability at 5 + Years	
	SMART 5+ Yr Follow-up Subjects N = XX
Number (%) of subjects reporting a re-intervention (lumbar procedure adjudicated as same location and etiology as Intracept procedure)	% (n/N)
Number (%) of subjects reporting actively using opioids (defined as > 25% of total prescribed dosage in 30 days prior to visit)	%(n/N)
Number (%) of subjects reporting low back pain injections in same treatment location as Intracept.	% (n/N)
Number (%) of subjects reporting less than 2 point decrease in pain (in same location) compared to baseline	% (n/N)
Number (%) of subjects reporting less than 10 point decrease in ODI compared to baseline	% (n/N)

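### The SAP narrows the protocol's opioid-use endpoint to use above 25% of dosage, with no rationale and no consistent denominator, so some daily users count as not active and pass the composite's opioid component

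*SAP*

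**What the plan says.** Protocol 5.2(e) defines the endpoint as "The proportion of patients currently utilizing opioids for low back pain of the same treatment region", and protocol 6.1 repeats it. Neither gives a dose threshold or a time window.

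SAP 3.1.2 keeps an endpoint for "subjects actively utilizing opioids for low back pain of the same treatment region" but defines active use as more than 25% of total dosage over 30 days. The same cut-off is one of five components of the SAP's composite of long-term treatment success: "Not actively using opioids for LBP (defined as $>$ 25% of total dosage used in 30 days prior to study visit". The sensible reading is that active use means more than 25% and that a patient at or below 25% passes.

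The denominator is worded in three ways:

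- total dosage, in the stand-alone endpoint (SAP 3.1.2) and in the success definition under Table 15;
- the same with the word *used* added, in the composite (SAP 3.1.2);
- prescribed dosage, in the Table 15 opioid row: "Number (%) of subjects reporting actively using opioids (defined as > 25% of total prescribed dosage in 30 days prior to visit".

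Table 12 pairs "Subjects Taking Opioids at Baseline" with "Subjects actively taking Opioids in last 30 days (5+ Year Follow-up Visit". Neither row states the 25% threshold.

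On data collection, protocol 7.4 says: "Drug type, prescribed dosage, and average daily dose for the last 30 days will be documented on the source document worksheet".

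**The concern.** A plain reader of the protocol endpoint would take current use to mean any current use. The SAP measures something else: the fraction of a reference dose that was consumed. That fraction is not opioid exposure, and a patient can take an opioid every day and stay at or below the cut-off.

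Two reported results depend on this: the proportion using opioids at 5+ years, and the composite success rate. There is no concurrent control at 5+ years, so a drop in opioid use that comes from the definition would not show up as a matching drop in a comparison arm. The paired rows in Table 12 add to the risk, because the term *actively* appears only in the follow-up row.

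**Working it through.** The documents give no opioid rate, sample-size figure or target for this endpoint, so there is no stated figure to reproduce. The check applies the SAP rule to illustrative patients and then asks which way the results can move. The doses below only show how the rule classifies; they carry no clinical recommendation.

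**Rule.** From the Table 15 row ("defined as > 25% of total prescribed dosage in 30 days prior to visit"): ratio = amount taken in 30 days / amount prescribed for 30 days. Active if ratio > 25%, otherwise not active.

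**Step 1: daily users.** With one tablet taken every day and k tablets a day prescribed, ratio = 30 / (30 × k) = 1/k.

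| Prescribed per day | Ratio | Class |
|---|---|---|
| 1 | 30/30 = 100% | active |
| 2 | 30/60 = 50% | active |
| 3 | 30/90 = 33.3% | active |
| 4 | 30/120 = 25.0% | not active |
| 6 | 30/180 = 16.7% | not active |
| 8 | 30/240 = 12.5% | not active |

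**Step 2: intermittent users at full prescribed dose.** Seven of 30 days is 7/30 = 23.3%, not active. Eight of 30 days is 8/30 = 26.7%, active.

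**Step 3: order of exposure.** For the same drug, 20 mg/day taken against 80 mg/day prescribed is 20/80 = 25.0%, not active, with 20 × 30 = 600 mg over 30 days. Taking 5 mg/day against 5 mg/day prescribed is 100%, active, with 5 × 30 = 150 mg. The patient classed as not active took four times as much (600/150).

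**Step 4: other denominators.** A patient with no current prescription has no denominator in Table 15, and the SAP gives no rule for that case. If total dosage meant the baseline dose, a daily user at or below 25% of that dose would still be not active. If the denominator were literally the amount used in the 30 days, every user would be at 100% and the threshold would do nothing. The wordings are not interchangeable.

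**Step 5: direction and bound.** Let f be the share of analysed patients whose use is above 0% and up to 25%, setting aside those with no denominator. Then:

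- reported use = any-use rate − f;
- composite success under the SAP − composite success with any use counted as failure ≤ f, because the ODI, pain, procedure and injection components must also be met.

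Neither result can move the other way.

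**Step 6: scale, by assumption only.** The documents do not give f. For assumed values of 2%, 5% and 10%:

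| Analysed N | f = 2% | f = 5% | f = 10% |
|---|---|---|---|
| 80 (assumed) | 1.6 patients | 4.0 | 8.0 |
| 133 (all eligible, protocol synopsis) | 2.7 | 6.7 | 13.3 |

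Reported use would be understated by 2, 5 or 10 percentage points, and composite success overstated by at most the same.

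**Step 7: Table 12.** If the baseline row means any use and *actively* in the follow-up row carries its SAP meaning, then with the same any-use rate U at both times the table would show U at baseline and U − f at 5+ years. That is an apparent fall of f with nobody having stopped.

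**The case against.** Several counter-arguments have force.

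- **The protocol does not say any use in 30 days.** Its wording is vague and the SAP is entitled to make it operational. This stands as far as it goes: any use is the plain reading, not the text. But a threshold that excludes some daily users is a narrowing that needs a reason, and none is given.
- **The composite is not in the protocol.** True. A reader might infer that the SAP inflates the composite against a protocol definition, but there is no such definition. The departure from the protocol concerns the stand-alone endpoint. In the composite, the issue is what its opioid component lets through.
- **The rule is disclosed.** The 25% appears in SAP 3.1.2 and Table 15, and the SAP says not actively using rather than not using. This stands, except that Table 12 does not repeat it and the denominator is not settled.
- **Table 12 may already show any use.** Its follow-up row states no threshold, and its dosage rows cover subjects taking opioids, whose n would be reported under SAP 4.1. If that group means any user, the any-use count would be visible. The SAP does not say so, and then *actively* would have two meanings across Tables 12 and 15.
- **The stakes are modest.** These are secondary endpoints, the opioid rows in Tables 12 and 15 carry no p-value, and the primary ODI result is untouched. This stands.

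A reader might also infer that the distortion is greatest in patients with the largest prescriptions. The documents do not support that: the cut-off is a ratio, nothing says the ratio varies with prescription size, and a patient on a small as-needed prescription taken on 7 of 30 days also falls below it.

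**Conclusion.** The point holds as a defect of endpoint definition and reporting. The SAP narrows a protocol secondary endpoint with an unexplained cut-off, states the denominator inconsistently, leaves patients without a prescription unclassified, and plans no clearly labelled any-use row at 5+ years. That daily users at or below 25% of their prescription are classed as not active, and pass the composite's opioid component, rests on the one Table 15 row that says prescribed. They count as treatment successes only if the other four components are also met.

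The direction is certain relative to any use: reported use is the same or lower, and composite success the same or higher. The size is not known. The 2 to 10 point range is an assumption, and for the composite it is an upper limit. The Table 12 concern is conditional on *actively* having its SAP meaning there. Nothing here bears on the primary endpoint, and the documents do not show that the resulting bias would be large.

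**What to change.** The change concerns endpoint definition and reporting only.

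1. In SAP 3.1.2, report the protocol endpoint as any opioid taken for low back pain in the 30 days before the visit, keeping the protocol's treatment-region qualifier.
2. In Table 12, use the same any-use definition in the baseline and 5+ year rows. Table 6 gives baseline opioid dose over 7 days, so if baseline use is available only for that window, label the difference.
3. Add an any-use row to Table 15, and report the composite also with any use counted as failure.
4. Keep the version above 25% as a labelled row with one reconciled denominator, a stated reason for 25%, and a rule for patients with no prescription.

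No new data are needed: the average daily dose on the follow-up worksheet already identifies any use. The cost is SAP wording and two or three extra table rows. The downside for the sponsor is that the opioid-use and composite success rates may look less favourable.
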